### 9.3.3. Outcomes definition

Outcomes will be identified during follow-up in outcome-specific analysis sets (except where noted) using diagnosis and procedure coding.

#### 9.3.3.1. Primary composite cardiovascular outcome

The primary composite cardiovascular outcome will evaluate the first occurrence of any of the following events during follow-up:

- An inpatient hospital diagnosis of fatal or nonfatal acute myocardial infarction [29]
- An inpatient hospitalisation with a primary diagnosis of heart failure [30]

Individuals with prior cardiovascular events are eligible for finerenone treatment; thus, those with an occurrence of these events before Time 0 may be included in the overall study cohort (before application of outcome-specific exclusion criteria). However, to ensure identification of cardiovascular outcomes that newly occur after Time 0, analysis of this composite cardiovascular outcome will be performed in an analysis set that also excludes individuals with an acute myocardial infarction diagnosis in the 365 days before Time 0. Those with a history of heart failure will be included in the analysis, and history of heart failure will be included.

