### 9.3.3.2.2. Hospitalisation for heart failure

Finerenone is indicated in the US to prevent hospitalisations for heart failure, among other events [13]. Hospitalisation for the heart failure outcome will identify the first occurrence of an inpatient hospitalisation with a primary diagnosis of heart failure [30] during follow-up. This analysis will include individuals with a history of heart failure before Time 0, and history of heart failure will be included as an adjustment variable. No outcome-specific exclusion criteria will be applied, but this outcome will be evaluated in the same analysis set as the primary composite outcome.

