#### 9.3.4. Covariate definitions

Covariates include risk factors for renal progression [39,40], cardiovascular outcomes [41,42], or hyperkalaemia [43-45]. Variables potentially associated with the use or non-use of finerenone and the outcomes of interest—e.g., concomitant medications, comorbidities—will be identified for all cohort members before or on Time 0 using diagnosis, procedure, or medication information available in the data source. A detailed description of definitions and code lists for all covariates that will be used in the data source will be specified in the SAP. Covariates will be defined using ICD-10-CM diagnosis codes, laboratory records, procedure coding, or medication coding, as appropriate for each variable.

The following demographic characteristics will be evaluated as of Time 0:

- Age
- Sex
- Calendar year of Time 0
- Race and/or ethnicity (as available in the data)
- Socioeconomic status (as available in the data)
- US geographic region
- Insurance plan type

The following clinical characteristics of patients will be defined using the 365 days before and including Time 0, except where specified otherwise:

- Markers of T2D severity (as available in the data source) and components of the Diabetes Severity Complications Index [46,47] not listed elsewhere
  - Duration of T2D (in all available lookback, as available in the data source)
  - Insulin use
  - Haemoglobin A1c (glycated haemoglobin) (HbA1c) (most recent recorded laboratory value in the 183 days before and closest to Time 0, if available)
  - Hyperosmolar hyperglycaemic state
  - Ketoacidosis

- Lower limb amputations (all available lookback, as available in the data source)
- Neuropathy
- Retinopathy
- Markers of kidney dysfunction severity
  - Duration of CKD (all available lookback, as available in the data source)
  - CKD stage, defined based on eGFR, or stage-specific diagnosis codes (using all available lookback) (Section 9.3.1)
  - Albuminuria stage defined based on UACR values (Section 9.3.1)
  - Proteinuria, defined based on diagnosis codes (Section 9.3.1)
  - Nephrotic syndrome, based on diagnosis codes (Section 9.3.1)
  - Glomerulonephritis
  - Renovascular disease
  - Polycystic kidney disease
  - Autoimmune disease
  - Gout/hyperuricaemia
  - Hospitalisation episodes for acute kidney injury

The following comorbidities will be defined using all available lookback before and including Time 0:

- Cardiovascular comorbidities
  - Acute myocardial infarction

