  - Atherosclerosis
  - Atrial fibrillation
  - Cerebrovascular disease (stroke or transient ischaemic attack)
  - Congestive heart failure
  - Hypercholesterolaemia
  - Hyperlipidemia
  - Hypertension
  - Peripheral vascular disease
  - Unstable angina
- Other components of the Charlson Comorbidity Index or similar comorbidity score [48,49] (as single entities, not listed elsewhere)
  - Anaemia
  - Chronic obstructive pulmonary disease
  - Congestive heart failure
  - Dementia

- Human immunodeficiency virus
- Liver disease
- Malignancy other than kidney cancer or nonmelanoma skin cancer
- Paralysis
- Other comorbidities
  - Coronavirus disease 2019 (COVID-19) diagnosis
  - Hyperkalaemia (history of hyperkalaemia, more than 90 days before Time 0)
  - Osteoporosis
  - Pneumonia

The following lifestyle cardiovascular factors will be defined, as available in the data:

- Body mass index or evidence of obesity
- Smoking status
- Alcohol abuse

The following healthcare utilisation measures will be identified in the 365 days before and including Time 0 to characterise patients' healthcare access, healthcare-seeking behaviour, and indicators of disease state at the time of index medication initiation:

- Healthcare utilisation
  - Hospital visits and hospital admissions
  - Emergency department visits
  - Long-term care or skilled nursing facility residence
  - Number of eGFR laboratory tests performed
  - Number of serum potassium laboratory tests performed
- Preventive health services
  - Influenza vaccination
  - Pneumococcal vaccination
  - COVID-19 vaccination
  - Bone mineral density test
  - Screening mammogram
  - Other cancer screening
- Frailty indicators [50]
  - Arthritis
  - Bladder dysfunction
  - Dementia
  - Psychiatric illness
  - Weakness
  - Vertigo

The following comedications will be identified in the 183 days before and including Time 0 to characterise individuals' recent treatments and indicators of disease state at the time of index medication initiation:

- Medications for T2D
  - Alpha glucosidase inhibitors
  - Dipeptidyl peptidase-4 inhibitors (DPP-4i)
  - GLP-1 RA
  - Meglitinides
  - Metformin
  - SGLT2i
  - Sulfonamides
  - Sulfonylureas
  - Thiazolidinediones
  - Insulin
- Cardiovascular medications
  - Angiotensin-converting enzyme inhibitors/angiotensin receptor blockers (ACEi/ARBs)
  - Aldosterone receptor blockers
  - Angiotensin receptor-neprilysin inhibitor
  - Anticoagulants

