### 9.7.4. Secondary outcome analyses

#### 9.7.4.1. Individual components of the composite cardiovascular outcome

For the separate secondary analyses of AMI and hospitalisation for heart failure, the same analysis set as that for the primary composite cardiovascular outcome will be used, with the same propensity score model. Each of the 2 outcomes will be evaluated separately; thus, follow-up may differ for the 2 outcomes. For each outcome, the weighted treatment group–

specific incidence rates, cumulative incidence plots, and overall HR will be estimated following the same methods as those for the primary outcome (Section 9.7.3).

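### Prior hospitalisation for heart failure, itself a component of the primary outcome, is not a listed baseline covariate; the only heart-failure-specific covariate is a history over all available lookback

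*Protocol*

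**What the plan says.** Protocol section 9.3.3.1 defines the primary composite as the first inpatient acute myocardial infarction (AMI) or the first hospitalisation with a primary diagnosis of heart failure. The two components are treated differently at baseline. For AMI, the analysis set "excludes individuals with an acute myocardial infarction diagnosis in the 365 days before Time 0". For heart failure there is no washout: "Those with a history of heart failure will be included in the analysis, and history of heart failure will be included". The sentence does not say what the history is included in. Section 9.3.3.2.2, on the heart failure component in the same analysis set, does: "history of heart failure will be included as an adjustment variable". Section 9.7.4.1 analyses the components "with the same propensity score model" as the composite, so one model serves all three analyses.

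In section 9.3.4 the heart failure covariate is "Congestive heart failure". It appears under both the cardiovascular comorbidities and the comorbidity-score components, under the rule "The following comorbidities will be defined using all available lookback before and including Time 0". No recency, count or admission measure is attached to it. The same section does list a cause-specific admission elsewhere: hospitalisation for acute kidney injury, in a 365-day window. Admissions in general are covered by "Hospital visits and hospital admissions" over 365 days, next to emergency department visits. Loop diuretics, neprilysin inhibitors, beta-blockers, digoxin and other mineralocorticoid receptor antagonists are listed over 183 days.

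**The concern.** With no washout for heart failure, control of prior heart failure rests on adjustment. A recent admission for the same event is plausibly a strong predictor of the next one. Under an all-lookback history, a patient coded once with stable heart failure years ago and a patient discharged last month after a heart failure admission both count as having the history. The covariate meant to control this does not separate them.

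The groups may differ on recent admissions. Under section 9.2.1.1 each finerenone user enters once, at the first prescription. Every eligible date with a recorded CKD diagnosis is a comparator entry, with repeats per person, so patients with much recent care can contribute more comparator records. In the other direction, section 9.9 itself raises the possibility that users have more advanced disease.

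The planned safeguards would not reliably reveal the problem. Section 9.7.2 checks balance on measured characteristics and refines the propensity model when those are out of balance; a variable that is not derived cannot trigger this. The negative controls first considered in section 9.7.7.1 (asthma visits, hand or finger laceration) are not aimed at heart failure severity. At stake are the primary hazard ratio and that of its heart failure component.

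**Working it through.** **1. The plan's own precision figures.** Inputs from section 9.5: RR 0.86, comparator risk q of 14.4% or 7.2%, 10 comparators per user, 95% CI. On the log-RR scale, with a = n1 × 0.86q events in n1 users and b = n0 × q events in n0 comparators:

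SE = sqrt(1/a − 1/n1 + 1/b − 1/n0), and P(upper limit < 1) = Φ(−ln 0.86 / SE − 1.96), where −ln 0.86 = 0.1508.

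- 30,000 records, 2,727 users, q = 14.4%: a = 337.7, b = 3,927.3, SE = 0.0530, probability 81.2% (83.2% by the pooled two-proportion formula).
- 60,000 records, 5,455 users, q = 7.2%: a = 337.8, b = 3,927.2, SE = 0.0549, probability 78.4% (80.2% pooled).

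The stated sizes for more than 80% reproduce within the tolerance of the method.

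**2. Random error at the expected size.** Section 9.5 expects at least 20,000 users. With 200,000 comparators at the same 10:1 ratio:

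- q = 14.4%: a = 2,476.8, b = 28,800, SE = 0.0196, half-width 1.96 × SE = 0.038 on the log scale.
- q = 7.2%: a = 1,238.4, b = 14,400, SE = 0.0287, half-width 0.056.

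This treats records as independent and unweighted, so the true intervals would be wider.

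**3. Bias from an unadjusted binary covariate.** The documents give neither the prevalence of recent heart failure admission nor its association with the outcome. Both are assumptions here. Let p1 and p0 be the prevalences in users and comparators that remain after weighting on the listed covariates, and r the risk ratio for such an admission given those covariates. Then

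B = [1 + p1(r − 1)] / [1 + p0(r − 1)],

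and the observed ratio is the true ratio times B.

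| p1 v p0 | r = 2 | r = 3 | r = 4 | 0.86 would read |
|---|---|---|---|---|
| 6% v 3% | 1.029 | 1.057 | 1.083 | 0.885 to 0.931 |
| 3% v 6% | 0.972 | 0.946 | 0.924 | 0.836 to 0.794 |
| 4% v 3% | 1.010 | 1.019 | 1.028 | 0.868 to 0.884 |
| 3% v 4% | 0.990 | 0.981 | 0.973 | 0.852 to 0.837 |

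Worked example: 6% v 3% with r = 3 gives 1.12 / 1.06 = 1.057, and 0.86 × 1.057 = 0.909.

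**4. Comparison.** For 6% v 3%, ln B runs from 0.029 (r = 2) to 0.079 (r = 4), in either sign. The half-widths in step 2 are 0.038 and 0.056. A bias of this size is of the same order as the random error at the expected size. For 4% v 3%, ln B runs from 0.010 to 0.027, below both half-widths.

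**The case against.** Four objections have weight.

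**Definitions are left to the SAP.** Section 9.3.4 defers detailed definitions and code lists, and section 9.1 has the SAP operationalise the variables. The protocol does not say that the heart failure covariate is a single yes/no, and the SAP may add recency. This stands in part. What is deferred is definitions and code lists; the list of covariates and their lookbacks are set in the protocol, and an earlier heart failure admission is not on that list although an acute kidney injury admission is. The variables for the censoring weights, by contrast, are expressly left to the SAP (section 9.7.3), so nothing is asked for there.

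**Recent severity is partly measured.** The stable patient and the recently discharged patient would ordinarily differ on all-cause admissions and probably on loop diuretics. This stands, and it is why the prevalences in the formula must be those left after weighting. It does not close the gap, because none of these measures separates a heart failure admission from another admission or from stable treated disease.

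**The direction is unknown.** A reader might infer a spurious benefit, because frequent users of care supply more comparator records. The documents do not support that: care intensity is itself covered by listed covariates, and the example in section 9.9 runs the other way, with more advanced disease in users raising their outcome rate. Nor do they show that heart failure hospitalisation is the main component of the composite. Section 9.5 gives component hazard ratios (0.78 and 0.91), not event counts.

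**The AMI contrast proves little.** Section 9.3.3.2.1 explains that exclusion as separating new events from continuing care, and keeping patients with heart failure is deliberate. The secondary new-onset heart failure analysis excludes any earlier heart failure diagnosis and so largely avoids the issue, but it is a different outcome in a subset and does not protect the primary hazard ratio.

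**Conclusion.** The point holds as a gap in a stated covariate list. Hospitalisation for heart failure is a component of the primary composite, and it can be measured at baseline with the outcome's own algorithm over the 365 days of enrolment that section 9.2.1.2 requires of every patient. It is neither excluded nor listed for adjustment. Residual confounding of the primary and heart failure hospitalisation hazard ratios is plausible, in either direction; the documents do not show that it will occur or which way it would go.

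The size is illustrative only. An imbalance of 3% v 6% left after weighting, with a 2- to 4-fold risk, shifts the ratio by about 3% to 8% either way; 3% v 4% shifts it by about 1% to 3%. The prevalences and risk ratios are assumptions. The change is worth making because it is cheap and because, at 20,000 or more users, random error is small enough for a bias of a few percent to matter. It affects bias, not the study size.

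**What to change.** 1. In section 9.3.4, add hospitalisation with a primary diagnosis of heart failure in the 365 days before Time 0, identified by the same algorithm as the outcome. Record it at least as yes/no, preferably by recency (for example 0–90 days, 91–365 days, none), alongside the existing heart failure history.
2. Include it in the propensity model shared by the primary composite and its components, and in the balance tables before and after weighting.
3. Complete the unfinished sentence in section 9.3.3.1 so that, as in section 9.3.3.2.2, heart failure history is stated to be an adjustment variable.

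Cost: protocol wording and one variable derived from inpatient claims already needed for the outcome. No new data are required. If the SAP already contains the variable, only the protocol text changes. The downside is slightly more variable weights if recent heart failure admission strongly predicts treatment.

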#### 9.3.3.2. Secondary outcomes

Secondary outcomes will include individual components of the primary composite cardiovascular outcome as well as additional safety and effectiveness outcomes of secondary interest.

### 9.3.3.2.1. Acute myocardial infarction

Finerenone is indicated in the US for the prevention of cardiovascular death and nonfatal acute myocardial infarction (AMI), among other events [13]. The AMI outcome will identify the first occurrence of an inpatient hospital diagnosis of fatal or nonfatal AMI [29] during follow-up. To ensure that AMI events identified during follow-up represent new events rather than continuing care for previous events occurring before Time 0, the analysis of this outcome will be performed in the same analysis set as the primary composite outcome, which also excludes individuals with an AMI diagnosis in the 365 days before Time 0.

### 9.3.3.2.2. Hospitalisation for heart failure

Finerenone is indicated in the US to prevent hospitalisations for heart failure, among other events [13]. Hospitalisation for the heart failure outcome will identify the first occurrence of an inpatient hospitalisation with a primary diagnosis of heart failure [30] during follow-up. This analysis will include individuals with a history of heart failure before Time 0, and history of heart failure will be included as an adjustment variable. No outcome-specific exclusion criteria will be applied, but this outcome will be evaluated in the same analysis set as the primary composite outcome.

### 9.3.3.2.3. New-onset heart failure

The US indication for finerenone includes the prevention of hospitalisation for heart failure, and the secondary hospitalisation for heart failure outcome (Section 9.3.3.2.2) will include individuals with a history of heart failure before Time 0. A secondary outcome will further evaluate new diagnoses of heart failure among individuals without a history of heart failure. The secondary new-onset heart failure outcome will evaluate the first occurrence of an inpatient hospital or emergency department diagnosis of heart failure [30] during follow-up. To ensure identification of new-onset heart failure, analysis of this outcome will be performed in an analysis set that also excludes individuals with a diagnosis of heart failure at any point before Time 0.

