- A diagnosis of adrenal insufficiency (i.e., congenital adrenogenital disorders of enzyme deficiency, primary or secondary adrenocortical insufficiency, Addison's disease, pituitary neoplasm, or other pituitary disorder [19]) at any time on or before Time 0 (days [-all available, 0]), as finerenone is contraindicated in individuals with adrenal insufficiency [13]
- Evidence of hepatic impairment, including hepatic failure, fibrosis, cirrhosis, or chronic hepatitis, at any time on or before Time 0 (days [-all available, 0]), as treatment with finerenone is to be avoided in individuals with severe liver impairment [13]
- An eGFR measurement < 25 mL/min/1.73 m^2 on or in the 90 days before Time 0 (days [-90, 0]), as finerenone is not recommended to be initiated in individuals with eGFR < 25 mL/min/1.73 m^2 [13]
- Evidence of recent increased serum potassium or hyperkalaemia, as finerenone is not recommended for initiation in individuals with elevated serum potassium [13], identified as either of the following:
  - A serum potassium test result > 5.0 mEq/L on or in the 90 days before Time 0 (days [-90, 0])
  - A diagnosis code indicating hyperkalaemia on or in the 90 days before Time 0 (days [-90, 0])
- Use of a strong CYP3A4 inhibitor on or in the 183 days before Time 0 (days [-183, 0]), as finerenone is a CYP3A4 substrate and is contraindicated in users of strong CYP3A4 inhibitors [13]. Examples include the following [20,21]:
  - Cobicistat
  - Itraconazole

- Ketoconazole
- Posaconazole
- Ritonavir
- Telithromycin
- Troleandomycin
- Voriconazole
- Evidence of pregnancy measured on or in the 40 weeks before Time 0, as clinical practice guidelines discourage the use of finerenone during pregnancy [16]

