### 9.2.1.3. Follow-up

Individuals will be followed-up from the day after Time 0 (i.e., day 1) until the first occurrence of 1 of the following:

- The date of an occurrence of the study outcome under evaluation (each outcome will be evaluated separately, and individuals may have different follow-up times for each outcome)
- Censoring at any of the following events:
  - End of the study period (i.e., end of available study data)
  - Loss to follow-up in the data source
  - Deviation from the treatment strategy defined on Time 0 for the primary analysis
    - Finerenone-exposed individuals discontinuing use of finerenone for reasons other than hyperkalaemia (pausing or discontinuing treatment for elevated serum potassium is consistent with treatment dose adjustment strategies [13]) or ESKD (discontinuing treatment for ESKD is consistent with treatment recommendations) [22]
    - Nonusers initiating finerenone

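### The AMI and new-onset heart failure washouts are worded without Time 0, so on a literal reading day 0 falls in neither washout nor follow-up

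*Protocol*

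**What the plan says.** Three parts of the protocol set the windows.

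- **Washouts.** The new-onset heart failure set "excludes individuals with a diagnosis of heart failure at any point before Time 0" (9.3.3.2.3). The primary composite set "excludes individuals with an acute myocardial infarction diagnosis in the 365 days before Time 0" (9.3.3.1). The AMI component uses the same set and repeats that it "excludes individuals with an AMI diagnosis in the 365 days before Time 0" (9.3.3.2.1). None of the three has a day bracket or names Time 0 as part of the window.
- **Follow-up.** Section 9.2.1.3 states: "Individuals will be followed-up from the day after Time 0 (i.e., day 1".
- **Covariates.** Section 9.3.4 states: "The following comorbidities will be defined using all available lookback before and including Time 0". The list that follows contains both acute myocardial infarction and congestive heart failure.

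The purpose of the AMI washout is that counted events "represent new events rather than continuing care for previous events occurring before Time 0" (9.3.3.2.1). The heart failure washout is likewise there so that onset is truly new. The new-onset event is the "first occurrence of an inpatient hospital or emergency department diagnosis of heart failure [30] during follow-up" (9.3.3.2.3), with no requirement that heart failure be the primary diagnosis.

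**The concern.** If the washouts are programmed as worded, day 0 belongs to no window that protects the outcome. A patient whose first heart failure code is entered at the Time 0 encounter carries heart failure as a baseline covariate, yet stays in the set meant to be free of it. An inpatient or emergency heart failure code in the following days is then counted as new onset. In the same way, an AMI first coded on day 0 stays in the primary set, and a further inpatient AMI record from day 1 becomes a primary event.

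Such events would fall early in follow-up. They would enter the hazard ratio and remain in the cumulative incidence at 6, 12 and 18 months. They need not be equally common in the two groups. A comparator Time 0 is any encounter with a CKD code, with no restriction on care setting, whereas an exposed Time 0 is a prescription or dispensing date (9.2.1.1, 9.3.2).

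**Working it through.** No figure in the plan depends on this point, so the check sets the windows side by side.

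| Item | Section | Wording on day 0 | Literal window |
|---|---|---|---|
| AMI washout (also primary set) | 9.3.3.1, 9.3.3.2.1 | not mentioned | [-365, -1] |
| Heart failure washout | 9.3.3.2.3 | not mentioned | [-all, -1] |
| AMI and heart failure covariates | 9.3.4 | included | [-all, 0] |
| Most disease exclusions | 9.2.1.2 | included, with bracket | ends at 0 |
| Follow-up | 9.2.1.3 | starts the day after | [1, ...) |

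An example of the exclusion style is "A diagnosis code indicating hyperkalaemia on or in the 90 days before Time 0 (days [-90, 0", where the text names Time 0 and the bracket ends at 0.

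1. Literal reading: the washout ends at day -1 and follow-up begins at day 1. Day 0 is uncovered.
2. Inclusive reading: the washouts become [-365, 0] and [-all, 0]. There is no gap, and they agree with the covariate windows.
3. Who is affected under reading 1: only Time 0s at which the first code within the window falls exactly on that date. A later comparator Time 0 of the same person has that code in its past, so it is washed out (for AMI, within 365 days).
4. Which outcomes are affected: new-onset heart failure, AMI, and the primary composite through its AMI part. Hospitalisation for heart failure has no heart failure washout by design, so it has no such gap.

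To see whether the direction of bias can be settled, take the primary composite with the inputs of section 9.5: comparator risk p0 = 14.4% or 7.2%, RR 0.86, p1 = 0.86 × p0. Let q be the share of Time 0s with a first code on day 0 and c the share of those with a counted event from day 1. Then

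observed risk = p + q × c × (1 − p).

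The documents give neither q nor c. I assume q = 1% and c = 25% to 50%, without weighting. Worked case, p0 = 7.2%, c = 50%, comparators only: 0.072 + 0.01 × 0.5 × 0.928 = 0.07664, and 0.06192 / 0.07664 = 0.808.

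| Affected at q = 1% | RR at 14.4% | RR at 7.2% |
|---|---|---|
| Comparators only | 0.847 to 0.835 | 0.833 to 0.808 |
| Both groups | 0.862 to 0.865 | 0.865 to 0.869 |
| Finerenone only | 0.875 to 0.890 | 0.893 to 0.925 |

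The sign depends on which group has more first codes on day 0. These figures show only that the direction is open. They are not an estimate of the bias.

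**The case against.** The strongest reply is that the protocol nowhere states a window ending at day -1. In 9.2.1.2 the enrolment criterion and the criterion of no earlier finerenone use both speak of time before Time 0 without adding the day itself, and both carry brackets that end at 0. The outcome washouts add to a list of exclusions applied on or before Time 0, and eligibility is evaluated on Time 0. Figure 1, which anchors the washout windows, is not visible in the text available, and operational definitions are left to the SAP.

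This stands as far as it goes: a reader might infer that the plan deliberately stops the washouts the day before Time 0, and the documents do not support that. It does not remove the ambiguity. In the two examples it is the bracket that brings day 0 in, and the washouts have none. The finerenone example is also a poor guide, because for the exposed group Time 0 is itself the first finerenone prescription. And the protocol, not only the SAP, fixes these windows and their purpose.

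A second reply is that weighting acts on the day-0 code, since it is a baseline covariate. In the heart failure set, on the literal reading, such records would be the only ones with that covariate present. Balancing their share would reduce a difference between groups but would leave the false events in both. In the AMI set the covariate does not separate a day-0 AMI from one more than 365 days old.

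A reader might also infer that the error favours finerenone, because comparator Time 0s are diagnosis-coded encounters. That is possible but not shown: the documents give no rate of day-0 codes in either group, and a new diagnosis may also prompt a finerenone prescription. Nor does the AMI washout define patients without any history, since AMI older than 365 days is allowed.

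**Conclusion.** The point holds as a defect of wording with a real consequence if it is programmed literally. Day 0 would then lie outside both washout and follow-up for AMI and new-onset heart failure, against the stated purpose of the washouts and out of line with the covariate windows for the same diseases. It reaches the primary outcome because the AMI washout defines that set. Size and direction are unknown. They depend on how often a first code falls on Time 0 in each group and how often counted care follows, and the protocol gives neither. If the inclusive reading was always meant, or Figure 1 already shows it, only the text needs to say so.

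**What to change.** Write the endpoints out:

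- AMI, in 9.3.3.1 and 9.3.3.2.1: on or in the 365 days before Time 0 (days [-365, 0]).
- Heart failure, in 9.3.3.2.3: on or before Time 0 (days [-all available, 0]).
- Make Figure 1 agree.

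This matches the style of 9.2.1.2 and the lookback in 9.3.4. It changes a few words in three sections. The downside is a small loss of records, namely those first coded on Time 0 itself. If day 0 was already intended, nothing in the analysis changes.
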